7.1. Time and Events Tables

This section consists of the Time and Events Tables and supplemental footnotes to describe assessment windows and sequencing of study-specific assessments and procedures.

7.1.1. Dose Escalation

7.1.1.1. Every 3 Weeks Dosing Schedule for Multiple Myeloma

Time and Events Table for Full Study (Cycle = 21 days)									
Study Assessments ¹	Screen ²	Day 1 C1	Day 2 C1	Day 8 C1	Day 15 C1	Day 1 C2	D1 of C3-C16	End of Study Treatment	3-Month Off-study Follow-up
Informed Consent	X								
Baseline Demographics	X								
Medical History	X								
Physical Exam	X	X				X	At the start of each cycle	X	
Ocular Exam	X ³					X ⁴	At the start of each cycle ⁴	X ⁴	
ECOG Performance Status	X					X	At the start of each cycle	X	
Vital Signs (BP, HR, Body Temperature)	X	X ⁵		X	X	X ⁵	At the start of each cycle ⁵	X	
Weight and Height	X	Weight only				Weight only	Weight only - At the start of each cycle	Weight only	
Hematology	X	X ⁶		X	X	X	At the start of each cycle	X	
Clinical chemistry	X	X ⁶	X	X	X	X	At the start of each cycle	X	
Urine Dipstick	X	X ⁶				X	At the start of each cycle	X	
INR, PTT	X	X ⁶		X	X	X	At the start of each cycle		
HBV/HCV tests	X								
CK-MB, Troponin	X ⁷			X ⁷		X ⁷	At the start of each cycle ⁷	X ⁷	
BNP	X ⁸								
UPEP and urine Immunofixation	X					X	At the start of each cycle		
SPEP and serum Immunofixation, Serum M- protein Calculation	X					X	At the start of each cycle		
Kappa, lambda free LC, FLC ratio	X					X	At the start of each cycle		
24 hr urine protein and albumin	X					X	At the start of each cycle		

Time and Events Table for Full Study (Cycle = 21 days)									
Study Assessments ¹	Screen ²	Day 1 C1	Day 2 C1	Day 8 C1	Day 15 C1	Day 1 C2	D1 of C3-C16	End of Study Treatment	3-Month Off-study Follow-up
IgG, IgM, IgA	X					X	At the start of each cycle		
CRP, beta2 microglobulin	X					X	At the start of each cycle		
Pregnancy Test	X ⁹						At the start of cycles 5 ⁹ , 9 ⁹ , 13 ⁹	X ⁹	X ¹⁰
Chest X-ray	X								
12-lead ECG	X ¹¹	X ¹¹		X ¹¹	X ¹¹	X ¹¹	At the start of each cycle ¹¹	X ¹¹	
LVEF and valves assessment (ECHO)	X ¹²						At the start of cycles 4 ¹² , 9 ¹²	X ¹²	
Extramedullary plasmacytoma imaging	X ¹³						At the start of cycles 5 ¹³ , 9 ¹³ , 13 ¹³	X ¹³	
BM Aspirate (see below for each test required within procedure):									
Disease assessment	X ¹⁴						At the time of Complete Response		
BCMA assessment and PD (flow)	X ¹⁵			X ¹⁵					
FISH testing	X ¹⁶								
BM biopsy for disease assessment and BCMA expression (IHC)	X ¹⁷						At the time of CR (disease assessment only)		
Serum (soluble BCMA)		X ¹⁸	X ¹⁸	X ¹⁸	X ¹⁸	X ¹⁸	Predose at the start of each cycle	X ¹⁸	
Serum (cytokines/chemokines)		X ¹⁹	X			X ¹⁹	At predose and EOI on D1 of each cycle	X	
Serum (anti-drug-antibodies)	X					X ²⁰	At the start of cycles 3 ²⁰ , 6 ²⁰ , 9 ²⁰ , 12 ²⁰ and 16 ²⁰	X	
Plasma-cfDNA	X							X	
Peripheral blood (flow for TBNK)	X ¹⁵					X ¹⁵	At the start of each cycle ¹⁵	X ¹⁵	
Serial Pharmacokinetics (blood)		X ²¹	X ²¹	X ²¹	X ²¹	X ²¹	C3D1 only ²¹	X ²²	
Urine PK	X ²³					X ²³	Day 1 of cycles 4 ²³ , 7 ²³ , 10 ²³ , 13 ²³ , 16 ²³		
Premedication if needed		X				X	At the start of each cycle		
GSK2857916 administration		X ²⁴				X ²⁴	X ²⁴		
Steroid eye drops		X ²⁵				X ²⁵	X ²⁵		
Adverse Events							Continuous		

Time and Events Table for Full Study (Cycle = 21 days)										
Study Assessments ¹	Screen ²	Day 1 C1	Day 2 C1	Day 8 C1	Day 15 C1	Day 1 C2	D1 of C3-C16	End of Study Treatment	3-Month Off-study Follow-up	
Concomitant Medications	X	Continuous								
Survival Status									X ²⁶	
Subsequent Treatment									X ²⁶	

- Assessments scheduled on days of dosing should be done prior to drug administration, unless otherwise specified. All other assessments can be ± 3 days of scheduled occurrence unless otherwise specified.
- All Screening assessments must be performed within 14 days prior to first dose unless otherwise specified. Informed Consent must be signed before any study-specific assessments are performed.
- Screening examination to include BCVA (best-corrected visual acuity), slit lamp examination (with special focus on cornea), intraocular pressure, and dilated fundoscopic examination may be performed within 21 days prior to first dose.
- On-study exams to include BCVA (best-corrected visual acuity) and slit lamp examination (with special focus on cornea); window for exams is up to 3 days prior to dosing.
- On initial (first infusion) dosing day, vital signs must be assessed at pre-dose (within 30 minutes prior to SOI), +10 minutes and +30 minutes (± 5 min) after SOI, EOI, and 1 hour post EOI. On subsequent dosing days, vital signs must be assessed at pre-dose (within 30 minutes prior to SOI), +30 minutes after SOI, and EOI. The Sentinel Subject must be observed for at least 24 hours post EOI. **On days where vital sign timepoints align with PK sampling timepoints, vital signs should be assessed prior to PK samples being drawn.**
- If completed within 72 hrs prior to the first dose, this assessment need not be repeated on Day 1 of Cycle 1. Refer to [Table 15](#) for comprehensive list of lab tests.
- Troponin will be measured at the local lab (troponin I or T) and a central lab (troponin I). CK-MB at the local lab or if not possible by a central laboratory.
- BNP to be measured locally, or if not available by a central laboratory, at screening; if cardiac workup is required due to safety concerns during the study, BNP should be measured.
- Perform only in women of child-bearing potential. A serum pregnancy test should be performed at screening, and subsequent pregnancy tests may be either serum or urine;
- Final pregnancy test (serum or urine) must be performed in women of childbearing potential 60 days after last study treatment.
- On dosing days, ECG to be performed in triplicate at predose (within 30 minutes prior to SOI) and EOI. **On days where ECG timepoints align with PK sampling timepoints, ECGs should be performed prior to PK samples being drawn (PK sample should be taken at the exact nominal time; refer to footnote 21).** At screening, on interim visits (C1D8 and C1D15) and End of Study obtain a single ECG measurement.
- At Screening, LVEF may be performed within 30 days prior to first dose. All ECHOs indicated on dosing days may be performed up to 5 days before dosing. All ECHOs to be done locally and sent to GSK for central imaging storage.
- May be performed up to 21 days prior to C1D1 as screening value. Needs to be performed by the same method throughout the study as was done at baseline (i.e. if PET scan was used as baseline, subject needs to be followed by PET scans). Selected target lesion needs to be measured and followed over time.
- Samples from within 14 days prior to first dose are acceptable.
- Sample(s) collected for analysis by central lab. The same sample will be used for BCMA (flow) and PD during Screening. On D8 only postdose PD assessment will be performed
- FISH testing at least for: t(4;14), t(14;16), 17p13del. FISH results from samples taken within 60 days prior to first dose are acceptable.

17. Archival tissue from up to 60 days prior to study is acceptable
18. A single sample for sBCMA will be collected at C1D8, C1D15 and at the End of Study visit. sBCMA samples will also be collected on C1D1 at predose (within 30 minutes prior to SOI), at EOI (± 5 minutes) and on C1D2 24h post SOI. On C2D1 sBCMA will be collected pre-dose (within 30 minutes prior to SOI) and at the EOI (± 5 minutes)
19. Collect cytokines at predose (within 30 minutes prior to SOI) and EOI (± 5 min) (even when infusion is interrupted or halted) to assess allergic reaction)
20. All ADA samples will be collected prior to each infusion
21. PK samples to be taken (in all subjects) for both GSK2857916 and cys-mcMMAF measurement: C1D1 at pre-dose (within 30 minutes prior to SOI), 0.5 h after the start of the infusion (SOI) (± 5 min), at the end of infusion (EOI) just before EOI, 1 h after EOI, 3 h after EOI (± 5 min), 8 h after EOI (± 15 min), 24h after EOI (± 1 h) (Day 2); C1D8 1 sample; C1D15 1 sample; C2D1, at pre-dose (within 30 minutes prior to SOI) and at the EOI (just before EOI); C3D1 at pre-dose (within 30 minutes prior to SOI) and at the EOI (just before EOI).
22. Collect 1 PK sample at each subject's final visit.
23. Pre-specified amounts of urine will be collected for PK analysis from the 24 hour urine collection at Screening, C2D1, C4D1, C7D1, C10D1, C13D1, and C16D1. Refer to Section 7.4.2 for details.
24. Study drug administration ± 3 day window only
25. Prophylaxis with prednisolone phosphate 1% or dexamethasone 0.1% 1 drop QID x 4 days starting 1 day prior to treatment
26. Record subject's survival status and whether subsequent treatment for disease was given. Subject does not need to come in for visit.

Abbreviations:

ADA = Antibody Drug Antibody; ALP = alkaline phosphatase; BCVA = best corrected visual acuity; BNP = B-type natriuretic peptide; C1D1 = Cycle 1 Day 1, etc.; cfDNA = Circulating free DNA; CK = creatinine kinase; CRP = C-reactive protein; EM = extramedullary; EOI = End of Infusion; FLC = free light chain; PD = Pharmacodynamics; PK = Pharmacokinetics; QID = 4 times a day; SOI = start of infusion; SPEP = serum protein electrophoresis; UPEP = urine protein electrophoresis

7.1.1.2. Weekly Dosing Schedule (Dose Escalation) for Multiple Myeloma

Time and Events Table for Full Study (Cycle = 28 days)									
Study Assessments ¹	Screen ²	Day 1 C1	Day 2 C1	Day 8 C1	Day 15 C1	Day 1 C2	D1 of C3-C16	End of Study Treatment	3-Month Off- study Follow-up
Informed Consent	X								
Baseline Demographics	X								
Medical History	X								
Physical Exam	X	X				X	At the start of each cycle	X	

Time and Events Table for Full Study (Cycle = 28 days)									
Study Assessments ¹	Screen ²	Day 1 C1	Day 2 C1	Day 8 C1	Day 15 C1	Day 1 C2	D1 of C3-C16	End of Study Treatment	3-Month Off-study Follow-up
Ocular Exam	X ³					X ⁴	At the start of each cycle ⁴	X ⁴	
ECOG Performance Status	X					X	At the start of each cycle	X	
Vital Signs (BP, HR, Body Temperature)	X	X ⁵		X	X	X ⁵	At the start of each cycle ⁵	X	
Weight and Height	X	Weight only				Weight only	Weight only - At the start of each cycle	Weight only	
Hematology	X	X ⁶		X	X	X	At the start of each cycle	X	
Clinical Chemistry	X	X ⁶	X	X	X	X	At the start of each cycle	X	
Urine Dipstick	X	X ⁶				X	At the start of each cycle	X	
INR, PTT	X	X ⁶		X	X	X	At the start of each cycle		
HBV/HCV tests	X								
CK-MB , Troponin	X ⁷			X ⁷		X ⁷	At the start of each cycle ⁷	X ⁷	
BNP	X ⁸								
UPEP and urine Immunofixation	X					X	At the start of each cycle		
SPEP and serum Immunofixation and Serum-M protein Calculation	X					X	At the start of each cycle		
Kappa, lambda free LC, FLC ratio	X					X	At the start of each cycle		
24 hr urine protein and albumin	X					X	At the start of each cycle		
IgG, IgM, IgA	X					X	At the start of each cycle		
CRP, beta2 microglobulin	X			X		X	At the start of each cycle		
Pregnancy Test	X ⁹						At the start of cycles 5 ⁹ , 9 ⁹ , 13 ⁹	X ⁹	X ¹⁰
Chest X-ray	X								
12-lead ECG	X ¹¹	X ¹¹		X ¹¹	X ¹¹	X ¹¹	At the start of each cycle ¹¹	X ¹¹	
LVEF and valves assessment (ECHO)	X ¹²						At the start of cycles 4 ¹² , 9 ¹²	X ¹²	

Time and Events Table for Full Study (Cycle = 28 days)									
Study Assessments ¹	Screen ²	Day 1 C1	Day 2 C1	Day 8 C1	Day 15 C1	Day 1 C2	D1 of C3-C16	End of Study Treatment	3-Month Off- study Follow-up
Extramedullary Plasmacytoma Imaging	X ¹³						At the start of cycles 5 ¹³ , 9 ¹³ , 13 ¹³	X ¹³	
BM Aspirate (see below for each test required within procedure):									
Disease assessment	X ¹⁴						At the time of Complete Response		
BCMA assessment and PD (flow)	X ¹⁵			X ^{15, 17}					
FISH testing	X ¹⁶								
BM biopsy for disease assessment	X ¹⁸						At the time of Complete Response (disease assessment only)		
Serum (soluble BCMA)		X ¹⁹	X ¹⁹	X ¹⁹	X ¹⁹	X ¹⁹	Predose at the start of each cycle	X	
Serum (cytokines/chemokines)		X ²⁰	X	X ²⁰	X ²⁰	X ²⁰	At predose and EOI on D1 of each cycle	X	
Serum (anti-drug- antibodies)		X ²¹			X ²¹	X ²¹	At the start of cycles 3 ²¹ , 6 ²¹ , 9 ²¹ , 12 ²¹ and 16 ²¹	X	
Plasma-cfDNA		X						X	
Peripheral blood (flow for TBNK and intracellular cytokine testing)		X ¹⁵		X ¹⁵		X ¹⁵	At the start of each cycle ¹⁵	X ¹⁵	
Serial Pharmacokinetics (blood)		X ²²	X ²²	X ²²	X ²²	X ²²	C3D1 only ²²	X ²³	
Urine PK	X ²⁴					X ²⁴	Day 1 of cycles 4 ²⁴ , 7 ²⁴ , 10 ²⁴ , 13 ²⁴ , 16 ²⁴		
Premedication if needed		X		X	X	X	Each dosing week		
GSK2857916 administration		X ²⁵		X ²⁵	X ²⁵	X ²⁵	Each dosing week ²⁵		
Steroid eye drops		X ²⁶		X ²⁶	X ²⁶	X ²⁶	Each dosing week ²⁶		
Adverse Events		Continuous							
Concomitant Medications	X	Continuous							
Survival Status									X ²⁷
Subsequent Treatment									X ²⁷

1. Assessments scheduled on days of dosing should be done prior to drug administration, unless otherwise specified. All other assessments can be done \pm 3 days unless otherwise specified.
2. All Screening assessments must be performed within 14 days prior to first dose unless otherwise specified. Informed Consent must be signed before any study-specific assessments are performed.
3. Screening examination to include BCVA (best-corrected visual acuity), slit lamp examination (with special focus on cornea), intraocular pressure, dilated fundoscopic examination may be performed within 21 days prior to first dose
4. On-study exams, to include BCVA (best-corrected visual acuity) and slit lamp examination (with special focus on cornea); window for exams is up to 3 days prior to dosing.
5. On initial (first infusion) dosing day, vital signs must be assessed at pre-dose (within 30 minutes prior to SOI), +10 minutes and +30 minutes (\pm 5 min) after SOI, EOI, and 1 hour post EOI. On subsequent dosing days, vital signs must be assessed at pre-dose (within 30 minutes prior to SOI), +30 minutes after SOI, and EOI. **On days where vital sign time points align with PK sampling timepoints, vital signs should be assessed prior to PK samples being drawn.**
6. If completed within 72 hours prior to first dose, this assessment need not be repeated on Day 1 of Cycle 1. Refer to [Table 15](#) for comprehensive list of lab tests.
7. Troponin will be measured at the local (troponin I or T) and central (troponin I) lab. CK-MB at the local lab or if not available by a central laboratory.
8. BNP to be measured locally, or if not available by a central laboratory, at screening; if cardiac workup is required due to safety concerns during the study, BNP should be measured.
9. Perform only in women of child-bearing potential. A serum pregnancy test should be performed at screening, and subsequent pregnancy tests may be either serum or urine.
10. Final pregnancy test (serum or urine) must be performed in women of childbearing potential 60 days after last study treatment.
11. On dosing days, ECG to be performed in triplicate at predose (within 30 minutes prior to SOI) and EOI. **On days where ECG timepoints align with PK sampling timepoints, ECGs should be performed prior to PK samples being drawn** (PK sample should be taken at the exact nominal time; refer to footnote 22). At screening and at End of Study, obtain a single ECG measurement.
12. At Screening, LVEF may be performed within 30 days prior to **first dose**; All ECHOs indicated on dosing days may be performed up to 5 days before dosing. **ECHOs to be done locally and sent to GSK for central imaging storage.**
13. **May be performed up to 21 days prior to C1D1** as screening value. Needs to be performed by the same method throughout the study as was done at baseline (i.e. if PET scan was used as baseline, subject needs to be followed by PET scans). Selected target lesion needs to be measured and followed over time.
14. Samples from within 14 days prior to first dose are acceptable.
15. Sample(s) collected for analysis by central lab. The same sample collected on Day 1 of cycle 1 prior to dosing will be used for BCMA (flow) and PD u.
16. FISH testing at least for t(4;14), t(14/16), 17p13del. FISH results from samples taken within 60 days prior to first dose are acceptable.
17. Collect sample prior to dosing.
18. Archival tissue from up to 60 days prior to study is acceptable.
19. A single sample for sBCMA will be collected at C1D8 predose, and at the End of Study visit. sBCMA samples will also be collected on C1D1 at predose (within 30 minutes prior to SOI), at EOI (\pm 5 minutes) and on C1D2 24h post SOI. On C1D15 and C2D1 collect at predose (within 30 minutes prior to SOI) and EOI (\pm 5 minutes)
20. Collect cytokines at predose (within 30 minutes prior to SOI) and EOI (\pm 5 min) (even when infusion is interrupted or halted) to assess allergic reaction
21. All ADA samples will be collected prior to each infusion
22. PK samples to be taken (in all subjects) for both GSK2857916 and cys-mcMMAF measurement: C1D1 at predose (within 30 minutes prior to SOI), 0.5 h after the start of the infusion, at EOI (just before EOI), 1 h after EOI (\pm 5 min), 3 h after EOI (\pm 5 min), 8 h after EOI (\pm 15 min), and 24h after EOI (\pm 1 h) (Day 2); C1D8 at predose (within 30 minutes prior to SOI), and at EOI (just before EOI); C1D15 at predose (within 30 minutes prior to SOI) and at EOI (just before EOI); C2D1 at predose (within 30 minutes prior to SOI), at EOI (just before EOI); C3D1 at predose (within 30 minutes prior to SOI) and at EOI (just before EOI).
23. Collect 1 PK sample at each subject's final visit.

24. Pre-specified amounts of urine will be collected for PK analysis from the 24 hour urine collection at Screening, C2D1, C4D1, C7D1, C10D1, C13D1, and C16D1. Refer to Section 7.4.2 for details.
25. Study drug administration ± 1 day window only.
26. Prophylaxis with prednisolone phosphate 1% or dexamethasone 0.1% 1 drop QID x 4 days starting 1 day prior to treatment
27. Record subject's survival status and whether subsequent treatment for disease was given. Subject does not need to come in for visit.

Abbreviations:

ADA = Antibody Drug Antibody; ALP = alkaline phosphatase; BCVA = best corrected visual acuity; BNP = B-type natriuretic peptide; C1D1 = Cycle 1 Day 1, etc.; cfDNA = Circulating free DNA; CK = creatinine kinase; CRP = C-reactive protein; EM = extramedullary; EOI = End of Infusion; FLC = free light chain; PD = Pharmacodynamics; PK = Pharmacokinetics; QID = 4 times a day; SOI = start of infusion; SPEP = serum protein electrophoresis; UPEP = urine protein electrophoresis

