The MTD (MTD1) or RP2D (RP2D1) established for GSK2857916 on Schedule 1 i.e., once every three weeks schedule, will inform selection of the starting dose for Schedule 2 i.e., the once weekly schedule. Additional cohort(s) may be enrolled to evaluate the safety, PK, and PD of GSK2857916 for the once weekly dosing schedule to establish an MTD2. GSK2857916 will be dosed once weekly for 3 consecutive weeks, followed by 1 week off (Schedule 2 = 28-day cycle).

- The once weekly dosing cohorts may be explored prior to, or in parallel with, enrollment to the expansion cohorts (Part 2).
- The dose escalation of the once weekly schedule will utilize a separate N-CRM model from the model used for the once every three week schedule. The information gained from the evaluation of the once every three week schedule (Schedule 1) will be utilized to more accurately define the N-CRM model used for dose escalation on the once weekly schedule (Schedule 2).
- Depending on emerging safety signals, the proposed weekly starting dose will be 25% of MTD1 or RP2D1. If the initial dose of 25% of MTD1 or RP2D1 is not tolerated, dose escalation on the weekly schedule will be terminated and enrollment into Schedule 2 will be closed. If the starting dose is tolerated, escalation on the weekly schedule will continue at increments of $\leq 30\%$ and will follow the N-CRM procedure until MTD2 or RP2D2 is reached.
- The MTD will be defined as that dose which has the highest probability of having a DLT rate within the target toxicity interval and for which the probability that the

DLT rate lies within the excessive toxicity or the unacceptable toxicity window is less than 25% (see Section 3.3.3 for DLT definitions). The DLT assessment period on Schedule 2 will be 28 days.

- The N-CRM procedure for the weekly schedule will not utilize a single subject/cohort run-in phase. Schedule 2 dose escalation cohorts will consist of 3 or more subjects due to higher starting dose and greater probability of toxicity.

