16.9.1.2. Dose Escalation: Weekly for Multiple Myeloma

Test Sample	Sample Volume	Screening	Cycle 1	Each Subsequent Cycle
Hematology	5 ml	5 ml	10-15 ml	5 ml
Chemistry	5 ml	5 ml	15-20 ml	5 ml
Coagulation	5 ml	5 ml	10-15 ml	5 ml
SPEP	6 ml	6 ml		6 ml
CRP	1 ml	1 ml	1 ml	1 ml
B2 Microglobulin	1 ml	1 ml	1 ml	1 ml
Kappa, lambda free LC, FLC	1 ml	1 ml		1 ml
IgG, IgA, IgM	6 ml	6 ml		6 ml
cfDNA	10 ml		10 ml	

Test Sample	Sample Volume	Screening	Cycle 1	Each Subsequent Cycle
Cytokines	3 ml		6 ml	6 ml
HBV/HCV	3 ml	3 ml		
CK-MB	3 ml	3 ml	3 ml	3 ml
ADA	3 ml		3 ml	0-3 ml
BNP	3 ml	3 ml		
Troponin	2.5 ml	2.5 ml	2.5 ml	2.5 ml
TBNK	6 ml		6 ml	6 ml
sBCMA	1 ml		6 ml	1-2 ml
Pregnancy Test ¹	2 ml	2 ml		0-2 ml
Total		43.5 ml	73.5-88.5 ml	48.5-54.5 ml

1. Required for women of childbearing potential

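### If the optional weekly schedule opens, two of every three doses from Cycle 2 on have no scheduled pre-dose blood count; adding one at the dosing visit is cheap

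*Protocol*

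**What the plan says.** Sections 3.3.2 and 3.8 of the protocol describe Schedule 2. It may be opened before or alongside Part 2, and gives one infusion a week for three weeks and then a week off, for at most 16 cycles and 48 doses. The stated plan is that "the proposed weekly starting dose will be 25% of MTD1 or RP2D1", with later steps of at most 30%. Section 3.3.2 adds that "Schedule 2 dose escalation cohorts will consist of 3 or more subjects due to higher starting dose and greater probability of toxicity" and that "The DLT assessment period on Schedule 2 will be 28 days".

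In the weekly escalation table (7.1.1.2), hematology, chemistry and INR/PTT fall on Days 1, 8 and 15 of Cycle 1 (chemistry also on Day 2) and on Cycle 2 Day 1. For Cycles 3-16 their entry is "At the start of each cycle", while the drug row reads "Each dosing week". Footnote 1 states: "Assessments scheduled on days of dosing should be done prior to drug administration, unless otherwise specified".

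The weekly expansion tables (7.1.2.2 and 7.1.2.4) have the same hematology pattern. Their only later mid-cycle safety panel is chemistry on Cycle 2 Day 15. They apply only if weekly dosing is chosen for Part 2.

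**The concern.** Several dose rules start from a laboratory value that the patient may not feel. Section 3.10.2 calls for a 25% reduction for Grade 3 platelets without bleeding, a hold for Grade 4 platelets, and a hold for a confirmed creatinine rise above 0.5 mg/dL. Grade 4 neutropenia without fever has no entry there, so Table 13 applies: permanent discontinuation if possibly drug-related. From Cycle 2, the protocol does not schedule the test that would trigger these rules before the Day 8 and Day 15 infusions.

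A second, narrower gap concerns dose finding. Some DLTs are laboratory findings. Section 3.3.3 counts the liver stopping criteria as DLTs, and in Section 3.9.1 ALT of at least 5 x ULN qualifies alone, with no symptom or duration condition. After the pre-dose sample on Cycle 1 Day 15, no routine panel is scheduled until Cycle 2 Day 1. Section 12.1 places the dose escalation meeting at the end of the DLT period.

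**Working it through.** **Later cycles.** The inputs are the 7.1.1.2 rows and Section 3.8.
- Total doses: 16 cycles x 3 = 48, which reproduces the protocol's figure.
- Doses in Cycles 2-16: 15 x 3 = 45. Scheduled pre-dose counts: 15 (Day 1 only). Without one: 45 - 15 = 30, and 30/45 = two of three.
- Share of all doses after k cycles: 2(k-1)/(3k). For k = 2, 2/6 = 33%; k = 4, 6/12 = 50%; k = 8, 14/24 = 58%; k = 16, 30/48 = 62.5%.
- Chemistry: also 30 in 7.1.1.2, and 30 - 1 = 29 in the expansion tables because of Cycle 2 Day 15.

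**DLT window in 7.1.1.2.**
- Panels on Day 15 (pre-dose) and Day 29 leave Days 16-28, or 13 days. If the ±1 day dosing window puts Cycle 2 Day 1 on Day 28, the run is Days 16-27, or 12 days.
- A Day 22 sample splits it into Days 16-21 and 23-28 (6 and 6). Taken on Day 21 the runs are 5 and 7; on Day 23, 7 and 5.
- Every-3-weeks hematology in Cycle 1 (Days 1, 8 and 15 of 21) has nominal runs of 6 days.

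**Dose intensity relative to MTD1 every 21 days**, assuming a start at 25% of MTD1 and maximum 30% steps.
- First cohort: (3 x 25%/28)/(100%/21) = 56%.
- Second: x 1.3 = 73%. Third: x 1.3² = 95%. Fourth: x 1.3³ = 124%.
- With cohorts of 3, the 15 subjects in Section 5.1 allow five cohorts. The roughly 9 in Table 3 allow three.

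**Blood in Cycle 1.** Appendix 10 ("Dose Escalation: Weekly for Multiple Myeloma") gives 43.5 mL at screening and at most 88.5 mL in Cycle 1, together 132 mL without PK. Its volumes omit draws that 7.1.1.2 and its footnotes require:

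| Test | Draws in 7.1.1.2, Cycle 1 | mL from table | mL in Appendix 10 | Difference |
|---|---|---|---|---|
| Cytokines | 7 (Day 1 x2, Day 2, Day 8 x2, Day 15 x2) | 21 | 6 | +15 |
| ADA | 2 (Days 1, 15) | 6 | 3 | +3 |
| TBNK | 2 (Days 1, 8) | 12 | 6 | +6 |

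- Cycle 1 is therefore up to 88.5 + 24 = 112.5 mL. Screening plus Cycle 1 is up to 43.5 + 112.5 = 156 mL, and with Day 22 up to 166 mL.
- Section 7 limits screening plus Cycle 1 to 162 mL. The 166 mL is an upper end: if the Day 1 hematology, chemistry and coagulation samples are skipped under footnote 6 (15 mL less), it is 151 mL.
- Footnote 22 gives 11 PK samples in Cycle 1, or 55 mL at 5 mL each. If PK counts toward the limit, 156 + 55 = 211 mL, already above it without Day 22.

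**Blood in later cycles.** Two visits x (5 + 5) mL = 20 mL. In Cycle 2 of the expansion tables it is 15 mL, because Day 15 chemistry is already there. On Appendix 10's escalation figures, 48.5-54.5 mL becomes 68.5-74.5 mL. The Section 7 limit does not cover these cycles.

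**The case against.** The best case against has four parts.

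1. *Schedule 2 is optional, and the expansion tables may never be used.* This stands. Amendment 5 put its new follow-up into the every-3-weeks expansion tables and left the 3-month column in the weekly ones, which suggests that Part 2 ran every three weeks. The point is conditional and rests mainly on 7.1.1.2.
2. *Investigators can test more often.* They can. Section 1.3.1 says blood counts will be checked often, Section 3.9.7 allows extra chemistry, and Section 7.3.7 requires abnormal results to be repeated. But the first two set no day, and the third needs an abnormal result first. Physical examination on dosing days, vital signs at each infusion and regular safety meetings do not reveal a silent value.
3. *The consequences in the DLT window are narrow.* Largely true. An abnormality escapes scheduled testing only if it is silent, arises after the Day 15 sample and resolves by Cycle 2 Day 1. The neutropenia DLT must also last at least 7 days, which one count cannot establish. The ALT criterion has no such condition, so the gap is real but secondary.
4. *Comparison with Schedule 1 flatters the point.* Partly true. With one dose per cycle, every Schedule 1 dose has a Day 1 count automatically, and after Cycle 1 its counts are 21 days apart. Its 24-hour urine is also first repeated after its DLT window. The comparison serves only for these panels within Cycle 1.

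A reader might go further and infer that DLTs will be undercounted and the weekly MTD set too high. The protocol gives no basis for estimating that: clinical DLTs are still captured as adverse events, and the Day 8 and Day 15 samples follow doses 1 and 2. A reader might also take Appendix 10 as proof of the reading, since it budgets one 5 mL hematology sample per later cycle. Given its mismatches with the table for cytokines, ADA, TBNK and PK, it is weak corroboration; the table rows carry the point.

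**Conclusion.** The main point holds as a cheap improvement, conditional on Schedule 2 opening. From Cycle 2, two of every three weekly doses (30 of 45 at the 16-cycle maximum) have no scheduled pre-dose count, while the protocol's own dose rules depend on such values. The same applies to 7.1.2.2 and 7.1.2.4 only if weekly dosing is chosen for Part 2. Footnote 1 is not itself wrong; it adds no test.

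The secondary point holds with less weight: 13 nominal days of the 28-day DLT window have no routine hematology, chemistry or INR/PTT. These figures measure scheduled opportunity to detect, not a rate of missed events, and assume visits on nominal days. The dosing windows move visits but add none.

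The low starting dose is a genuine offset early on. The 124% intensity should not be read as what Schedule 2 would deliver: it is an upper bound at a fourth cohort after three maximum steps, and intensity is 95% at the third.

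**What to change.** **Main change, before any subject is dosed weekly.** Add pre-dose hematology and chemistry on Days 8 and 15 of Cycles 2-16 in 7.1.1.2, and in 7.1.2.2 and 7.1.2.4 if weekly dosing is chosen for Part 2. The patient already attends for dosing. The cost is about 20 mL more blood per later cycle (15 mL in Cycle 2 of the expansion tables) and having results available before infusion.

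**Secondary change.** Add one Cycle 1 Day 22 (±1 day) hematology and chemistry sample in 7.1.1.2, with abnormal values repeated under Section 7.3.7 to establish duration. The cost is one short extra visit and 10 mL for up to 15 subjects. Because the table-based total can then reach 166 mL without PK, either raise the 162 mL limit or trim Cycle 1 research draws. State at the same time whether the limit includes PK, and bring Appendix 10 into line with the table.

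**Route.** A short amendment is the clean option. Section 7 also lets the sponsor approve and document added time points on newly available data without an amendment. Schedule 1 data may satisfy that condition, and the sponsor should decide.
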